Once processed, vocal features are extracted from the audio and inputted into the neural network models. The software interprets the acquired signals using signal processing and an artificial neural network to quantitatively evaluate voice characteristics for presence of indicators correlated to depression and anxiety. The Kintsugi Voice Device then generates an output for signs of depression and anxiety which is displayed to the Device Operator. The Kintsugi Voice Device output will be positive for depression or negative for depression and positive for anxiety or negative for anxiety. The outcome can also be “uncertain” or within an “indeterminate range” if the Device cannot provide a high-confidence result.

Study Objectives

This study seeks to evaluate the ability of the Device to aid clinical assessment for depression and anxiety by comparing its output with the established diagnostic standard consisting of a diagnosis made by a specialist clinician based on DSM-5 criteria.

This is a prospective study of up to 100 subjects, ages ≥ 22 years of age.

We are striving for a 50%/50% split of subjects who have depression and/or anxiety and subjects who do not have depression and/or anxiety.

Study Endpoints

Effectiveness Endpoints

The primary endpoints of this study are to:

1. Determine the specificity and sensitivity of the Device in discriminating the presence of a significant depressive episode using the Structured Clinical Interview for DSM-5 Clinical Trial Version as the established diagnostic standard (“gold standard”)
2. Determine the specificity and sensitivity of the Device in discriminating the presence of a clinically significant anxiety state using the SCID-5-CT as the established diagnostic standard

The secondary endpoints of this study are:

- Measurement of the percentage of all adults for whom the Device provided no result
- Determine the specificity and sensitivity of the Device in discriminating the presence of a significant depressive episode compared to the PHQ-9
- Determine the specificity and sensitivity of the Device in discriminating the presence of a clinically significant anxiety state compared to the GAD-7

Safety Endpoints

Adverse events (AEs) and serious adverse events (SAEs) will be collected and reported from enrollment, which is determined by informed consent signature, through the completion of the study.

Study Duration

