The study is expected to last up to 8 months. The duration of each individual subject’s involvement in the study will be approximately 2 hours total consisting of a screening call followed by a psychiatrist clinical evaluation and online survey. However, participants could be active on the study for up to 2 weeks to schedule a SCID assessment.

Study Design and Procedures

This is a prospective fully remote, decentralized clinical study to measure the sensitivity and specificity of the Device predictions against clinical ground truth for major depressive disorder and for generalized anxiety disorder. Up to 100 participants will undergo investigational and comparator assessments for major depressive disorder and a clinically significant anxiety state.

The research coordinator will schedule a time with the participant for the evaluation. There will be a two-part evaluation: a web-based study survey and a specialist clinician evaluation via the SCID assessment. The SCID assessment will include questions about the past medical history of the participant as well as questions from the Clinical Global Impression - Severity scale. The order of the two evaluations will be randomized to minimize any potential bias.

The Device output will be positive for depression, negative for depression, or indeterminate for depression and positive for anxiety, negative for anxiety, or indeterminate for anxiety. PHQ-9 and GAD-7 scores will also be collected through the Study Survey.

Participants will also be evaluated by a specialist clinician via the SCID assessment. The psychiatrist performing the SCID assessment will be a board-certified psychiatrist. The clinical evaluation via the SCID assessment will be recorded and the channel-separated audio file of the participant during this assessment will be used as the Device input. The input for the Device will be obtained by the clinical research team and will be at least one minute of audio taken from the SCID assessment where the participant is asked about their current illness history and treatment history. The results of these assessments will act as the clinical comparator for comparison with the Device output.

Clinicians and participants will both be blinded to the participant the Device output and the participant assessment results (SCID, PHQ-9, GAD-7). Further, a SCID reviewer may review the recorded SCID assessment and standard clinical assessment and completed SCID template to minimize interrater variability.

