The participant will be given access to the informed consent form. The informed consent form serves to ensure that participants understand the purpose of the study, assessments the participants will be asked to undertake as part of the study, the risks and benefits of participating, and the voluntary nature of their participation. The informed consent form will inform the participants that they will provide a recording of their voice and video as part of the study. The informed consent form will also inform the participants that their specialist SCID assessments conducted over a HIPAA-compliant video-conferencing platform will be recorded for the purposes of the study and research. A copy of the consent form will be provided to the participant after they consent. A clinical research coordinator will be available to answer participant questions about the study.

Randomization

The order in which the online survey and SCID assessment occur will be randomized. All participants will participate in investigational (Kintsugi Voice Device) and comparator assessments (SCID assessment, PHQ-9, and GAD-7).

Figure 2: Study Design Flow

A schematic of the study steps is illustrated in Figure 2.

Participants will be considered enrolled once they have signed the informed consent form.

Participants will receive instructions on completing our web-based Study Survey. If the audio sample from the SCID assessment is not scorable (e.g. poor microphone quality, insufficient length, excessive background noise), the participant may be asked to submit an additional audio sample. A clinical research team member will run the audio sample through the Device. Participants will fill out the PHQ-9 and GAD-7 questionnaires as part of the Study Survey. The Device output, PHQ-9, and GAD-7 results will not be shared with the clinicians. Similarly, the Device output, the PHQ-9, and GAD-7 results will not be shared with the participants.

Participants will complete a SCID assessment immediately after or immediately before the web-based Study Survey. A clinical research coordinator will be available to support the participant if they run into issues with the Study Survey.

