Participants may feel discomfort answering questions or being interviewed.

An emergency contact will be collected for each participant, in the rare case that there is imminent danger to the participant as determined by the psychiatrist and, as stated in the consent, that 911 may be called if the clinician determines there is an emergency. The clinician will refer the participant to local resources should there be an emergency but will not provide ongoing care.

Potential Benefit

Knowledge gained from the study could potentially benefit patients in the future.

Participation in this study might lead to identification of clinically significant depression or clinically significant anxiety, enabling earlier therapy known to positively impact outcomes.

Adverse Events Reporting

Definitions

Term	Definition
Adverse Event (AE)	Any untoward medical occurrence, unintended disease or injury, or untoward clinical signs (including abnormal laboratory findings) in participants, users or other persons, whether or not related to the investigational Device (ISO 14155-1).
Serious Adverse Event (SAE)	Adverse event that a) Led to death, b) Led to serious deterioration in the health of the participant, that either resulted in 1) A life-threatening illness or injury, or 2) A permanent impairment of a body structure or a body function, or 3) In-patient or prolonged hospitalization, or 4) Medical or surgical intervention to prevent life-threatening illness or injury or permanent impairment to a body structure or a body function, c) Led to fetal distress, fetal death or a congenital abnormality or birth defect (ISO 14155-1).
Anticipated Serious Adverse Device Effect (ASADE)	An anticipated serious adverse Device effect (ASADE) is any SAE on health or safety or any life-threatening problem or death caused by, or associated with the Device, if that effect, problem, or death was previously identified in nature, severity, or degree of incidence in the investigational plan, informed consent, operator manual, other risk analysis documentation or regulatory application; or any other serious problem associated with a Device that relates to the rights, safety, or welfare of subjects.

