Unanticipated Serious Adverse Device Effect (USADE)	Any serious adverse effect on health or safety or any life-threatening problem or death caused by, or associated with, a Device, if that effect, problem, or death was not previously identified in nature, severity, or degree of incidence in the investigational plan or application (including a supplementary plan or application), or any other unanticipated serious problem

	associated with a Device that relates to the rights, safety, or welfare of participants 21 CFR 812.3(s).
--	--

Recording of AEs/ADEs and SAEs/SADEs

All suspected adverse events (AEs) will be evaluated and recorded in the participant’s study case report form. The AEs/ADEs/SAEs/SADEs may be observed by the investigator and/or clinical research staff or volunteered by the subject. All observed and volunteered adverse signs and symptoms, anticipated or unanticipated, regardless of severity or frequency will be recorded in the case histories (i.e. case report form). The reports of the AEs/ADEs/SAEs/SADEs will include the description of the event or symptom, date of onset, date of resolution, severity, anticipated or unanticipated, the relationship to the study Device, the action taken (if any), and the outcome. AEs/ADEs will be reported to the IRB only if the study clinicians, [name] and [name], determine that the event is possibly or definitely related to the Device. All SAEs/SADEs, anticipated or unanticipated, must be reported to the sponsor and reviewed by the IRB as soon as possible, but no later than 10 working days after the initial event was recorded. The study clinicians, [name] and [name], will review all adverse events to determine the severity and relationship to study Device.

Follow-up of Subjects after AEs

All reported AEs/ADEs/SAEs/SADEs should be followed until resolution of the event or until the subject’s participation in the study ends. Resolutions of the events should be documented in the appropriate case report form.

Data Analysis Plan

This is a prospective study with up to 100 subjects who meet the inclusion criteria and who do not meet any of the exclusion criteria.

The analysis set includes all enrolled subjects who provide a sample of their voice and are evaluated by a specialist. Device-related adverse events will be tabulated and analyzed.

Study Management

Investigator, Clinician, and Research Staff Selection

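### The safety endpoint covers all AEs and SAEs from consent, but the one safety-analysis sentence names only the Device-related subset

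*Protocol*

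**What the plan says.** Under Study Endpoints, Safety Endpoints, the protocol states: "Adverse events (AEs) and serious adverse events (SAEs) will be collected and reported from enrollment, which is determined by informed consent signature". Collection continues to study completion, and relatedness is not mentioned.

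Under Adverse Events Reporting, Definitions, an adverse event counts "whether or not related to the investigational Device".

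Under Data Analysis Plan, the only sentence on safety analysis is "Device-related adverse events will be tabulated and analyzed". The sentence directly before it defines the only analysis set: "The analysis set includes all enrolled subjects who provide a sample of their voice and are evaluated by a specialist". No separate safety set is named.

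Two statements bear on how many events could be Device-related. Study Design and Procedures says of the recorded SCID interview that "the channel-separated audio file of the participant during this assessment will be used as the Device input". The text below the study flow figure (Figure 2) says "A clinical research team member will run the audio sample through the Device", and that the output is shared with neither clinicians nor participants.

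Under Potential Risks, the protocol calls risk minimal, names loss of confidentiality as the main risk, and adds: "Participants may feel discomfort answering questions or being interviewed". It also provides for the rare psychiatric emergency.

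**The concern.** An endpoint and its analysis should have the same scope. Here the endpoint is all events and the analysis is the part attributed to the Device. A report written to the letter of the Data Analysis Plan would not summarise the endpoint the protocol set.

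The choice of subset matters in this design. Participants do not operate the Device and never see its result, whereas they do sit through a psychiatric interview and complete two symptom questionnaires. The burden of taking part lies mainly in those procedures, so a summary restricted to Device-related events looks where few are likely to be found.

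Entry to the summary would also depend on a judgement of relatedness by the study clinicians. A table of all events that shows relatedness as a column does not depend on that judgement in the same way.

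**Working it through.** There is no figure to reproduce. The protocol states no expected adverse event rate and no safety sample size, so the check is a comparison of text.

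**Step 1: scope of the endpoint.** Safety Endpoints covers AEs and SAEs from consent to completion. The AE definition excludes any test of relatedness. Scope: all events, in everyone who has consented.

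**Step 2: scope of the analysis.** The Data Analysis Plan covers Device-related adverse events. Scope: a subset of step 1.

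**Step 3: what falls between them.** Write all events as the sum of two parts:

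N(all) = N(Device-related) + N(other)

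The stated tabulation shows N(Device-related). The part of the endpoint without a stated summary is N(all) − N(Device-related) = N(other). This can lie anywhere from 0 to N(all), and the protocol gives nothing to narrow that range numerically.

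**Step 4: which part is likely to be larger.**

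| Feature of the design | Where stated | Bearing on relatedness |
|---|---|---|
| Device input is audio from the recorded interview | Study Design and Procedures | The Device adds little contact with the participant beyond the interview |
| Staff run the audio through the Device | Text below Figure 2 | The participant does not operate it |
| Output withheld from participants and clinicians | Text below Figure 2 | The result cannot upset a participant or alter care in the study |
| Discomfort from questions or interview is possible | Potential Risks | Arises from study procedures |
| Rare psychiatric emergency | Potential Risks | Arises from the participant's condition or the interview |

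The first three rows leave the Device little route to cause an event. The last two describe events that would ordinarily be judged unrelated to the Device. It is reasonable to expect N(Device-related) to be small. This is an inference from the design; the protocol does not state it.

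**Step 5: who is counted.** Collection starts at consent, but the only analysis set requires a voice sample and a specialist evaluation. If that set is also used for safety, an event in someone who consents and stops before completing the interview could be left out as well.

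**Step 6: what is protected elsewhere.** Under Recording of AEs/ADEs and SAEs/SADEs, all suspected AEs go into the case report form, however mild or infrequent. Each is described by severity and relationship to the Device, among other items. All SAEs, whatever their cause, go to the sponsor and are reviewed by the IRB within 10 working days. Non-serious events go to the IRB only if judged possibly or definitely Device-related. A non-serious event not attributed to the Device would thus be recorded, but would reach neither the IRB nor the stated tabulation.

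**The case against.** The strongest reply is that the sentence does not say that nothing else will be tabulated. Safety Endpoints separately commits to collecting and reporting all AEs and SAEs. The two can be read together: everything is reported, and Device-related events are also tabulated and analysed. The layout of safety tables is commonly left to the statistical analysis plan, which was not available here and may already include a full table.

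Much of this stands. The restriction is a reading of the only safety-analysis sentence, and the protocol does not forbid a wider table. But the objection treats the point as a missing detail, when the protocol has stated a scope and that scope is narrower than its endpoint. An analysis plan written to follow the sentence could inherit the gap.

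A second reply is that related events may not be so rare. The IRB reporting rule uses possible as well as definite relatedness, and the definitions of serious device effects reach problems associated with the Device, including those touching rights and welfare. A confidentiality breach involving the audio might be classed that way. That also stands, and it is why the subset is called likely to be small and not empty.

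A reader might go further and infer that the plan would report essentially no events whatever happened in the interviews, or that it misses events the protocol expects. The documents do not support either. All AEs are recorded and all SAEs are reported regardless of cause. Discomfort is something participants may feel, not something predicted, and ordinary unease at a question need not meet the definition of an AE. Any specific count of omitted events would rest on a rate the protocol does not give.

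**Conclusion.** The point holds as a mismatch of scope within the protocol: the endpoint is all AEs and SAEs from consent, and the one stated safety analysis is the Device-related subset. Non-serious or procedure-related events that the protocol foresees could be missing from the planned summary. Nothing is lost from the case report forms, and serious events still reach the sponsor and the IRB.

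The size cannot be put in numbers. In direction, the omitted part is probably the larger share of whatever events occur. That rests on two assumptions: that relatedness is judged in line with how the Device is used here, and that no unseen analysis plan already widens the table. No accuracy endpoint is affected. This is a worthwhile tidy-up in a study of up to 100 participants at minimal risk, not a serious flaw.

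**What to change.** Replace the safety sentence in the Data Analysis Plan with wording to this effect: all AEs and SAEs occurring from consent to the end of the study, in all consented subjects, will be tabulated by seriousness, severity and relationship to the Device, with Device-related events shown as a subset.

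Naming all consented subjects keeps the safety summary separate from the analysis set that requires a voice sample and a specialist evaluation.

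The cost is one sentence and one table. The AE/SAE classification, severity and relationship to the Device are already collected, so no new data are needed. A separate category for events related to study procedures would be informative but is optional. Relationship is now recorded to the Device alone, so that category would need one added case report form field and a corresponding judgement by the study clinicians.
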